Category 1: Research not involving greater than minimum risk.

E2. Subjects

Gender:
Both

Age:

Geriatric (65+ yrs)

Ethnicity:

All Ethnicities

Primary Language:

English, Spanish

Groups to be recruited will include:

Patients

Which if any of the following vulnerable populations will be recruited as subjects?

Vulnerable populations require special protections. How will you obtain informed consent, protect subject confidentiality, and prevent undue coercion?

E3. Pregnant woman/fetus

Will pregnant women and/or fetuses (as described in 45 CFR 46 Subpart B) be enrolled in the research?

No

E4. Neonates

Will neonates of uncertain viability or nonviable neonates (as described in 45 CFR 46 Subpart B) be enrolled in the research?

No

E5. Children

Will children be enrolled in the research?

No

Section F: Design/Procedure

F1. Design

Select one category that most adequately describes your research:

c) Pilot

Discuss the research design including but not limited to such issues as: probability of group assignment, potential for subject to be randomized to placebo group, use of control subjects, etc.

For this research design there are two phases.

Phase I: 15 subjects with mild dementia and cognitive impairments will participate in a single arm 6 weeks remote exercise intervention.

Phase II: 100 subjects with mild dementia and cognitive impairments will participate in a randomized controlled trial (RCT) exercise intervention using two arms for 12 weeks. The control group will perform the exercise intervention in a supervised condition and the intervention group will perform the exercise intervention remotely.

Inclusion Criteria:

Male and female patients with MCI and mild dementia (formal diagnosis or MoCA score between 20-26), who are ambulatory (able to walk a distance of 20m with or without walking assistance), living independently in a residential home with a caregiver/informant, and who are willing and able to provide informed consent, will be recruited.

Exclusion Criteria:

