Phone calls: We will contact subjects at three and six months after their follow up visit to ask if they have had any accidental falls and other questions regarding their health. Research Coordinators may also call subject for study related questions.

Photos and media: We will be asking permission of the subject to take photos, film videos and/or record audio during the visits in order to monitor their progress throughout the study. Additionally, these photographs might be used for scientific publications/ oral presentations. If the subject's face is in the photo, as per journal policy, we will cover their face.

Phase II: The study will consist of a 12 week exercise program with one baseline, 24 exercise sessions, 6 weeks follow up, 12 weeks follow up, 6 months follow up, and 12 month follow up.

The same questionnaires and physical assessments will be completed at each in person visit as Phase I. In Phase II, 100 subjects will be randomized into either intervention or control group. All recruited subjects will undergo to 12 weeks exercise program using the Exergaming platform described in the proposal, twice per week for approximately 30 minutes. The intervention group will be given the Exergaming system and will perform the 24 exercise sessions remotely. The control group will perform the exercise sessions in person under supervision with the Exergaming system. The first four sessions (week #2), subjects are asked to perform six blocks (each approximately takes 5 min to be completed) of consecutive ankle reaching tasks in upward-downward (i.e. ankle flexion-extension) direction and side-ward reaching task (foot inversion-eversion). They could have reset between each block of exercise before starting the next block. Starting the 5th session (week #4), reaching tasks on diagonal directions are added, which is required the combined foot inversion-eversion and ankle flexion-extension. To keep the duration of exercise constant, a block from simple reaching task is replaced by a new complex reaching task. From the 11th session (week #6), motor-cognitive tasks as described in the following will be added. The tasks make the program more challenging and fun, in addition to potentially having a secondary benefit for older patients who may struggle to execute motor-cognitive tasks.

Section G: Sample Size/Data Analysis

G1. Sample Size

How many subjects (or specimens, or charts) will be used in this study?

Local: 115 Worldwide: 115

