Please indicate why you chose the sample size proposed:

For Phase I: Considering the timeline and budget limitation, the sample size is limited to 15 subjects. Size was estimated based on preliminary study, described in detail in the research strategy document, in which we have demonstrated that 4-weeks exergame program significantly reduce center of mass (COM) sway in aMCI patients with an effect size of 0.83 compared to baseline. Assuming a pairwise comparison using t-test, 80% power, alpha of 5%, 14 subjects should be sufficient to observed significant difference in balance compared to baseline. For phase II: The sample size was calculated based on our preliminary study described above for training-related improvement in balance (quantified by CoM sway area in medial-lateral direction during eyes-open stance), fear of falling (quantified by FES-I), and cognitive function (quantified by TMT) post exercise in people with confirmed amnestic MCI. Our preliminary results suggested that prior Exergame, COM sway in was 1.60 ± 0.76 cm² and was improved to 1.05 ± 0.44 cm² post Exergame intervention (Cohen's effect size $d=0.83$). Assuming a pairwise comparison using t-test, 80% power, alpha of 5%, 14 subjects should be sufficient to observed significant difference in balance compared to baseline. Our preliminary study has also suggested that FES-I was significantly improved post exercise compared to baseline with an effect size of 1.14, suggesting a sample size of 9 to

observe benefit for fear of falling. Finally, effect size for improvement in TMT A post exercise was 0.42. Thus using similar assumptions described above, the needed sample size for observing benefit for cognitive function is 46. Assuming approximately 10% drop out, we plan to recruit 50 subjects per group, for a total of 100 subjects.

G2. Data Analysis

Provide a description of your plan for data analysis. State the types of comparisons you plan (e.g. comparison of means, comparison of proportions, regressions, analysis of variance). Which is the PRIMARY comparison/analysis? How will the analyses proposed relate to the primary purposes of your study?

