(For both phases) We will used paired t-test (for normally distributed outcomes) and Mann-Whitney U-tests (for non-parametric outcomes) to determine the effect of intervention at 6 weeks. To examine whether the benefit of exercise is dependent on sex (sex as biological factor), we will compare the gain in balance improvement between male and female using Mann-Whitney U-test. We recognize that the study is under power for assessing the effect of confounders (e.g. age, baseline cognitive performance, baseline motor performance, BMI, etc). However, we determine whether the magnitude of gain is correlated with any of these confounders using Spearman correlation of coefficient change. During Phase II, these confounders will be controlled as covariant and between and within group comparisons will be adjusted.

Section H: Potential Risks/Discomforts

H1. Potential Risks/Discomforts

Describe and assess any potential risks/discomforts; (physical, psychological, social, legal, or other) and assess the likelihood and seriousness of such risks:

The measuring systems including LEGSys (for assessing gait and balance), BalanSens (for assessing balance), and PAMSys (for monitoring spontaneous daily physical activities) , as well as the iTMT platform are battery-powered, self-contained units and used in many clinical studies including patients with MCI and AD, and no adverse report were reported. Except activity monitoring, the rest of assessments including gait and balance will be performed in a control environment. As these devices are attached using elastic straps, research staff will ensure these are comfortably tight on the participant to avoid any pain or poor blood flow.

For home assessment, PAMSys (will be used for daily physical activity monitoring and daily motor performance such as postural transition) is worn in a shirt or vest pocket and does not rest directly against subjects' skin. Thus, wearing the PAMSys, poses no risks to subjects. All wearable sensors, which will be used in this study meet the requirements for IDE exemption under 21 CFR 812.2(c), Category 3.

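### Phase II randomises remote against supervised exercise, but its sample size and stated test concern change within an arm; the planned between-arm comparison is not named primary and has no effect, power or precision attached

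*Combined protocol and SAP*

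**What the plan says.** Section F1 describes the Phase II arms: "The control group will perform the exercise intervention in a supervised condition and the intervention group will perform the exercise intervention remotely". Section F2 adds: "In Phase II, 100 subjects will be randomized into either intervention or control group". Both arms use the same exergame platform for 12 weeks, with follow-up at 6 and 12 weeks and at 6 and 12 months.

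Section G1 takes its Phase II size from a preliminary study of change after training. It assumes a paired t-test, 80% power and 5% alpha. It gives 14 subjects for COM sway (effect size 0.83) and 9 for FES-I (1.14). For TMT-A (0.42) it says: "Thus using similar assumptions described above, the needed sample size for observing benefit for cognitive function is 46". It then concludes: "Assuming approximately 10% drop out, we plan to recruit 50 subjects per group, for a total of 100 subjects". For sway it also prints means and SDs: "COM sway in was 1.60 ± 0.76 cm² and was improved to 1.05 ± 0.44 cm² post Exergame intervention".

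The G2 form asks: "Which is the PRIMARY comparison/analysis". The answer, given for both phases, is a paired t-test, or Mann-Whitney U for non-parametric outcomes, "to determine the effect of intervention at 6 weeks". The arm comparison appears in one clause. After listing confounders that include baseline cognitive and baseline motor performance, G2 says that in Phase II "these confounders will be controlled as covariant and between and within group comparisons will be adjusted".

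**The concern.** Both arms receive the exergame, so improvement from baseline in either arm cannot show whether remote delivery does as well as supervised delivery. Randomisation protects only the comparison between arms. The sizing figures and the test that G2 spells out address the other question.

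A reader of G1 sees 80% power beside 50 per group and cannot tell what that number delivers for remote against supervised. With no primary outcome, visit or contrast fixed, two poor outcomes are possible. A within-arm improvement could be reported as the trial's result. Or a non-significant arm difference could be read as showing that the two modes of delivery are equivalent, when the interval is too wide to say so.

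**Working it through.** **1. Reproduce G1.** Paired t-test, two-sided 5%, noncentral t with noncentrality d√n and n−1 df:

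- d = 0.83, n = 14: power 81.9%
- d = 1.14, n = 9: power 84.9%
- d = 0.42, n = 46: power 79.6% (47 is needed to pass 80%)

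A two-sample t-test at the same three effects would need 24, 14 and 90 per arm. So 14, 9 and 46 are within-arm numbers, and for that question the arithmetic is sound to within one subject.

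**2. Completers.** 50 × 0.90 = 45 per arm.

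**3. Unadjusted comparison of change, any outcome.** The standard error is SD of change × √(2/45) = 0.211 SD, with 88 df. The 95% CI half-width is 1.987 × 0.211 = 0.42 SD. The difference detectable at 80% power is 0.60 SD.

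**4. TMT-A: remote delivery loses the whole 0.42 gain.** G1 does not say which SD the 0.42 is divided by, so both readings are shown. Assumptions: equal SDs before and after, and pre-post correlation r of 0.3 to 0.7; the documents give neither. The SD of change is √(2(1−r)) raw SDs. The residual SD after baseline adjustment (ANCOVA, 87 df) is √(1−r²) raw SDs, which is √((1+r)/2) SDs of change.

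| r | 0.42 in SDs of change: unadjusted | adjusted | 0.42 in raw SDs: unadjusted | adjusted |
|---|---|---|---|---|
| 0.3 | 50% | 69% | 38% | 54% |
| 0.5 | 50% | 62% | 50% | 62% |
| 0.7 | 50% | 57% | 72% | 79% |

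**5. COM sway.** Inputs from G1: SD 0.76 before and 0.44 after, applied to both arms. The correlation is not given. If 0.83 is mean change over SD of change, then the SD of change is 0.55/0.83 = 0.663 and r = (0.76² + 0.44² − 0.663²)/(2 × 0.76 × 0.44) ≈ 0.50. But 0.83 also fits another definition. The pooled SD is √((0.76² + 0.44²)/2) = 0.621 and 0.55/0.621 = 0.886. A small-sample correction for 7 per time point (the pilot size in section H1), 1 − 3/47 = 0.936, gives 0.83. On that reading r is unknown, so a range is needed.

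The adjusted residual SD is 0.44√(1−r²), which is 0.420 at r = 0.3 and 0.314 at r = 0.7. Multiplying by 0.597 gives a detectable difference of 0.25 to 0.19 cm². Multiplying by 0.419 gives a half-width of 0.18 to 0.13 cm². Power to detect loss of half the sway effect (0.55/2 = 0.275 cm²) is 87-98% adjusted and 40-65% unadjusted.

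These figures worsen if the weaker arm keeps a wider spread after training. With a post SD of 0.60 or 0.76 in that arm (assumed) and r about 0.50, the adjusted detectable difference is about 0.27 or 0.32 cm².

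**6. FES-I.** No SDs are given, so no adjusted figure can be computed. Loss of half the effect (1.14/2 = 0.57), read as SDs of change, has 76% power unadjusted.

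**The case against.** **Adjusted between-group comparisons are already planned.** This stands. The G2 covariates include baseline cognitive and motor performance, so for TMT-A and sway some baseline adjustment is the natural reading, and the unadjusted figures are a reference point rather than the planned analysis. What remains open is whether each outcome is adjusted for its own baseline, at which visit, and which comparison is primary. The mention of Mann-Whitney U, a two-sample test, does not settle this: it is offered as the alternative to the paired test in both phases, including single-arm Phase I.

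**The study is labelled a pilot, and its aim is to design and validate a technology.** This could justify sizing by precision. But G1 argues from 80% power and states no precision. It is also true that G1 claims no between-arm power and says plainly that the sway and FES-I figures are against baseline.

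**Other material may hold the missing figures.** G1 refers to a research strategy document that is not available here. The point is therefore limited to this form.

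**Tempting stronger readings.** A reader might infer that Phase II is underpowered and needs 90 completers per arm. That number uses 0.42 as a between-arm difference, and the documents give no such difference. A reader might also take 50% as the trial's power. It is one value in a range, for one outcome, and depends on how 0.42 was scaled. For sway, adjusted power may be good.

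**Conclusion.** The point holds for what is sized and what is named, not as a finding that N is too small. All of G1's Phase II figures describe paired change within an arm. The randomised comparison is foreseen in one clause, with no outcome, visit, effect, power or precision attached.

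What 50 per group delivers between arms depends heavily on choices the plan leaves open. Across the assumptions above, power to detect complete loss of the TMT-A gain runs from 38% to 79%, while adjusted power to detect loss of half the sway effect is 87-98% if the printed SDs hold in both arms. The equal SDs for TMT-A, the correlation range, the 45 completers and the scale of 0.42 are assumptions or readings, so these figures should be used as ranges. That the sizing is within-arm, and that this form names no primary comparison, is certain. This should be fixed, and wording is enough.

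**What to change.** Keep N at 100.

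**In G2:**
- Name one primary outcome (COM sway, FES-I or TMT-A) and one follow-up visit for Phase II.
- Make the primary analysis the between-arm difference adjusted for that outcome's own baseline (ANCOVA, or a mixed model over visits), in all randomised participants, with a 95% CI.
- State whether the aim is to test for a difference, to estimate it as a pilot, or to show that remote is no worse; in the last case, give and justify the margin.
- Treat within-arm changes as descriptive, and say that a non-significant arm difference will not be read as equivalence.

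**In G1:**
- Label 14, 9, 46 and the 80% as within-arm only, and say which SD each effect size uses.
- Add the between-arm detectable difference and CI half-width for the named outcome under its adjusted analysis, as a range over stated SDs and correlations. For sway this would be about 0.19-0.25 cm² detectable and a half-width of 0.13-0.18 cm² (SDs 0.76 and 0.44, r 0.3-0.7), with a note that both are larger if one arm's post SD exceeds 0.44.

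This costs no patients or visits. The price is a less favourable stated power for Phase II, mainly for TMT-A, and a commitment to one outcome and one visit.

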Rapid population aging is increasing the number of older adults who suffer from motor-cognitive declines and associated increases in fall risk and fear of falling. Effectiveness of exercise, as an effective intervention to preserve cognitive function, has been well established and supported by recent studies including systematic reviews and our own prior work. But at the same time individuals with poor motor and cognitive performance generally cannot have regular visits to a rehabilitation center for face-to-face exercise, have highest drop out because of functional limitations, and have poorest adherence to unsupervised exercise programs. Therefore, designing a remote exercise intervention, tailor for those with cognitive impairment, is desperately needed and could make a significant impact in the field, including preserving cognitive function in people with MCI, promoting independent living, and reducing costs associated with consequence of cognitive-motor decline including falls and frailty. We propose to develop an in-home exercise system for adults with mild cognitive impairment or mild dementia that is specifically designed to improve balance and cognition during distractive conditioning while the exercise is remotely supervised by a telemedicine interface.

Section D: Purpose and Objectives

This research study aims to help design and validate a novel technology to remotely provide exercise intervention for people at risk or with some level of dementia. In addition, the platform enables remote assessment of cognitive-motor performance via wearable sensors through playing a simple interactive game named iTMT. A remote exercise intervention tailored to those with cognitive impairments could make significant impact in preserving cognitive function in people with MCI, promoting independent living, and reducing costs associated with consequence of cognitive-motor decline including falls and frailty. This application could in addition further the knowledge in use and development of remote technology to screen cognitive and motor performance and promote independent living in older adults in particular for those who are suffering from cognitive impairment and dementia. Given the large and growing number of older people at risk of developing cognitive impairment and dementia, this knowledge would be important to health providers, clinicians, older people, and their caregivers.

Section E: Protocol Risks/Subjects

E1. Risk Category

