This is a longitudinal study of 'care-as-usual' with supplementary minimum risk virtually guided foot and ankle motor-cognitive exercises. We believe that there are no significant psychological, legal, or social risks. Participation is entirely voluntary and the participants could stop/leave the study at any time. All exercise programs are administered while standing but the subject will have a research staff member or caregiver (during Phase II, remote intervention arm) and thus potential risk of fall is minimum. However, like any exercise, some may feel joint pain associated with consecutive foot and ankle joint rotation. To minimize the fatigue and risk of joint pain, exercises are divided to several blocks of maximum 5 min. Subjects will have enough rest before initiating the next block of exercise. There may be some concerns or stress due to potential "failure" to successfully complete an exercise task. To minimize the risk, the first few sessions include simple motor-cognitive tasks and the complexity level increases as the exercise progresses. In our pilot program, in which 7 subjects participated in the Exergame intervention program (twice per week for 4 weeks), only one subject was dropped out due to travelling difficulties, while all other participants completed all exercise sessions. No adverse events or concerns about difficulties of the exergame tasks were reported.

Please note that there is also the possibility for loss of confidentiality. The PI and the research team will minimize the possibility of for loss of confidentiality by keeping all the physical data locked in cabinets only accessible to the research team. The electronic data will be kept on network password protected institutional computers. . Data collected during the study may be published and made publicly available. Data may also be shared with other research groups. However, data that could in any way identify the subject will not be made public or shared. And, subject PHI will be coded as much as possible to minimize the potential for loss of confidentiality.

H2. Data and safety monitoring plan

Do the study activities impart greater than minimal risk to subjects?

No

H3. Coordination of information among sites for multi-site research

Is the BCM Principal Investigator acting as the SPONSOR-INVESTIGATOR for this multi-site research?

No or Not Applicable

Is BCM the COORDINATING CENTER for this multi-site research?

No or Not Applicable

Section I: Potential Benefits

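### Does recruiting 50 per group in Phase II fall short of the plan's own requirement of 46 once 10% drop out?

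*Combined protocol and SAP*

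**What the plan says.** Section G1 (Sample Size) bases Phase II on pre-to-post effect sizes from a preliminary study. For balance the effect is 0.83: "Assuming a pairwise comparison using t-test, 80% power, alpha of 5%, 14 subjects should be sufficient". For fear of falling the effect is 1.14, with a need for 9. For cognition, "effect size for improvement in TMT A post exercise was 0.42", and on the same assumptions "the needed sample size for observing benefit for cognitive function is 46". This is the largest of the three requirements, so it sets the size of Phase II. The section then allows for dropout: "Assuming approximately 10% drop out, we plan to recruit 50 subjects per group, for a total of 100 subjects". It does not say whether the test is one- or two-sided, what the effect was before rounding, or how the allowance was applied.

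Two other places bear on dropout. Section H1 reports that in a four-week pilot with 7 participants "only one subject was dropped out due to travelling difficulties". The background says that people with poor motor and cognitive performance "have highest drop out because of functional limitations".

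**The concern.** The dropout step appears to contradict the line before it. If 46 completers are needed and a tenth are lost, 50 recruits leave 45. TMT-A alone fixes the sample size, so the 80% power would be missed under the plan's own inputs. An exact calculation at 0.42 makes this slightly worse, because it asks for 47 rather than 46. Dropout could also exceed 10%: the pilot lost 1 of 7 in four weeks because of travel, while Phase II lasts 12 weeks and one arm attends all 24 sessions in person. At stake would be an overstated power claim for the outcome that determines recruitment.

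**Working it through.** **Inputs (all from G1).** Paired t-test, alpha 5%, power 80%, effect d = 0.42 for TMT-A, about 10% dropout, 50 recruited per group. Two-sided testing is inferred, as step 1 shows.

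**1. Reproduce the plan's figures.** Power comes from the noncentral t distribution with n − 1 degrees of freedom and noncentrality d√n.

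| Effect | Plan | Exact, two-sided | Exact, one-sided | Normal approximation, two-sided |
|---|---|---|---|---|
| 0.83 | 14 | 14 | 11 | 12 |
| 1.14 | 9 | 9 | 7 | 7 |
| 0.42 | 46 | 47 (fractional 46.45) | 37 | 45 |

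The 14 and 9 identify the method as the exact two-sided test. On that method 0.42 gives 46.45, which rounds up to 47. The printed 46 corresponds to rounding down, or to an unrounded effect slightly above 0.42. From about d = 0.4222 upwards, 46 reaches 80%, and every value from there to 0.4249 prints as 0.42. The documents therefore do not show that 46 is wrong.

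**2. Apply the dropout allowance.**
- 50 × 0.90 = 45 completers.
- Correct inflation of 46: 46/0.90 = 51.1, so 52 per group.
- A likely route to 50 (an inference): 46 × 1.10 = 50.6, rounded down.
- Losses that still leave 46: 50 − 46 = 4, and 4/50 = 8%.

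**3. Power around the target (exact, two-sided).**

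| Completers | d = 0.415 | d = 0.42 | d = 0.4249 |
|---|---|---|---|
| 45 | 77.7% | 78.7% | 79.6% |
| 46 | 78.6% | 79.6% | 80.5% |
| 47 | 79.5% | 80.5% | 81.4% |
| 50 | 82.0% | 82.9% | 83.8% |

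At 45 completers and d = 0.42 the shortfall is 80 − 78.7 = 1.3 points. The effect that gives 80% at 45 is 0.427, only 0.007 above the planned value.

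**4. Compare that 0.007 with the uncertainty in 0.42.** G1 does not give the size of the preliminary study, so a range is assumed. The standard error of a paired effect size is roughly √(1/n + d²/(2n)).
- n = 6 (if it is the pilot in H1, with 6 completers): √(0.1667 + 0.0147) = 0.43.
- n = 46 (a generous assumption): √(0.0217 + 0.0019) = 0.15.

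Even in the generous case the standard error is about twenty times 0.007.

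**5. Does the pilot contradict 10%?** One loss in 7 is 14%, with an exact 95% interval of about 0.4% to 58%. If true dropout were 10%, the chance of at least one loss among 7 is 1 − 0.9⁷ = 52%. The pilot does not argue against 10%.

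**The case for a change.** The best case for a correction runs as follows. The plan's own method is the exact t-test, so the normal approximation cannot be used to justify 45. No effect that rounds to 0.42 rescues 45 either, since 0.4249 still gives only 79.6%. If losses occur independently at 10% (an assumption), the chance of keeping at least 46 of 50 is 43% in one arm and 19% in both. Nothing in the documents supports a rate of 10% or lower. If the pilot's 1 in 7 recurred, 50 × 6/7 = 42.9, about 43 completers, and power would be 76.8%. The remedy is a few words in G1.

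The arithmetic stands: at exactly 10% loss, 50 per group is one short of 46 and power is just under 79%. The rest carries less weight. The 76.8% rests on one person. The travel argument leaves out the benefits described in Section I: parking or transport is compensated for the in-person group, each exercise session and assessment visit is paid, and the remote group needs no clinic visits beyond baseline screening and the post-exercise evaluation. G2 places the test of the intervention effect at 6 weeks, so losses after that do not reduce its sample. The background sentence on dropout gives no rate and serves to motivate the remote programme. Even the unfavourable figure of 76.8% is about 3 points below target.

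Phase I adds nothing. Its 15 is attributed to time and budget and exceeds the 14 required, and G1 claims no dropout allowance for it.

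**Conclusion.** No change is needed. The dropout allowance was rounded in the wrong direction: 52 per group follows from 46, and 50 was chosen. Read literally, that costs one completer per group and 1.3 points of power. This is within what is left open by an effect printed to two decimals and a dropout rate given as approximate, and far inside the uncertainty of the preliminary estimate. Replacing 46 with 47 would assert an error that the documents cannot establish. Wording that says about 79% instead of 80%, with 100 still recruited, would alter no procedure, analysis or conclusion. If G1 is edited for another reason, about 79% power with about 45 completers per group would be the more exact statement.

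This rests on two-sided testing, which the plan's 14 and 9 imply, and on the paired within-group comparison that G1 specifies. It does not endorse that comparison as the basis for Phase II. Using a within-group size to plan a randomised comparison of two exercise arms is a larger and separate question, which two more recruits per group would not settle.

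### Single-arm Phase I has only paired before-after data, but section G2 names the Mann-Whitney U-test, an independent-samples test, as its fallback for non-normal outcomes

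*Combined protocol and SAP*

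**What the plan says.** Section G2 (Data Analysis) opens with a rule that covers Phase I as well as Phase II: "We will used paired t-test (for normally distributed outcomes) and Mann-Whitney U-tests (for non-parametric outcomes"). Its stated aim is to assess what the exercise programme has achieved by week 6.

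Section F1 describes Phase I as follows: "15 subjects with mild dementia and cognitive impairments will participate in a single arm 6 weeks remote exercise intervention". There is no second group.

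Section G1 sizes Phase I as a paired comparison with baseline: "Assuming a pairwise comparison using t-test, 80% power, alpha of 5%, 14 subjects should be sufficient". The figures behind it are "COM sway in was 1.60 ± 0.76 cm² and was improved to 1.05 ± 0.44 cm² post Exergame intervention", with a stated effect size of 0.83.

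G2 then uses the Mann-Whitney test a second time: "we will compare the gain in balance improvement between male and female using Mann-Whitney U-test". That use is sound, because men and women are independent groups and the quantity compared is each person's gain. For Phase II, G2 adds that "between and within group comparisons will be adjusted" for the listed confounders. No signed-rank or other paired rank test appears anywhere in the document.

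**The concern.** The rule pairs a within-person test (paired t) with a between-group test (Mann-Whitney) as if the second were the distribution-free version of the first. In Phase I the only available 6-week contrast is each participant against their own baseline, so an analyst who follows G2 for a non-normal outcome would compare 15 baseline values with 15 follow-up values as though they came from 30 different people.

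When a person's two values are positively correlated, this overstates the variability of the change, so a real improvement can be missed. G1 needs 14 people and plans 15, which leaves little room for lost power. The 80% power in G1 is stated for a paired t-test and does not carry over to a Mann-Whitney analysis.

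In Phase II the point is narrower. A Mann-Whitney test between the two arms would be valid, so the concern reaches only an unadjusted rank test within an arm.

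**Working it through.** **Inputs.** From G1: baseline sway 1.60 (SD 0.76), follow-up 1.05 (SD 0.44), effect size 0.83, 80% power, alpha 5% (sidedness not stated). From F1 and G1: 14 people required, 15 planned. The documents give no pre-post correlation r.

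**Step 1: the plan's own figure.** A two-sided paired t-test at 5% with d = 0.83 needs n = 13.44 for 80% power, which rounds up to 14. Power is 81.9% at n = 14 and 84.8% at n = 15. The plan's 14 is reproduced.

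**Step 2: a value for r.** If 0.83 is mean change over the SD of the differences:

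- SD of differences = (1.60 − 1.05)/0.83 = 0.55/0.83 = 0.663
- r = (0.76² + 0.44² − 0.663²)/(2 × 0.76 × 0.44) = (0.5776 + 0.1936 − 0.4391)/0.6688 ≈ 0.497

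This supports r = 0.5 as a working value, but it remains an assumption. If the pilot described in H1 (7 enrolled, 1 dropout) is the source, 6 completers give a 95% interval for r of about −0.53 to 0.93. A range of r is therefore shown.

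**Step 3: why ignoring the pairing costs power.** The variance of a change is SD₁² + SD₂² − 2r·SD₁·SD₂. An unpaired test drops the last term. Here that gives 0.771 instead of 0.439, a ratio of about 1.76.

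**Step 4: power of the two rank tests.** Correlated pairs were simulated with the G1 means and SDs, n = 14 and 15, using exact two-sided 5% tests (up to 60,000 replicates per setting). At r = 0.5:

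| Data | Mann-Whitney | Signed-rank | Loss (points) |
|---|---|---|---|
| Normal | 62-64% | 80-83% | about 19 |
| Lognormal | 69-71% | 89-91% | about 20 |
| t, 5 df | 74-76% | 85-88% | about 12 |
| t, 3 df | 88-90% | 92-93% | about 4 |

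For normal and lognormal data, across other correlations:

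| r | Loss (points) |
|---|---|
| 0 | none (Mann-Whitney slightly ahead) |
| 0.3 | about 9-11 |
| 0.7 | about 23-28 |

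With normal data the loss is about 30 points at r = 0.8 to 0.9. If the paired effect size of 0.83 is held fixed instead of the raw means and SDs, the loss is about 25 points at r = 0.5 and about 50 at r = 0.7.

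**Step 5: sample size equivalent.** At r = 0.5, Mann-Whitney reaches 80% power with about 20 completers (normal) or 18 (lognormal), against 15 planned.

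**Step 6: type I error of Mann-Whitney at nominal 5%, r = 0.5.** It is about 1% with equal SDs and about 1.4-3% with SDs of 0.76 and 0.44. The test is conservative when r is positive.

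**The case against.** The strongest reply accepts the naming error and disputes its weight.

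- **The rank test is only a fallback.** The loss of about 20 points compares the two tests as if each were always used. G2 gives no rule for judging normality. If it were a Shapiro-Wilk test at 5% on the differences (n = 15, r = 0.5), the rank test would be used in about 5% of normal and 22-24% of lognormal trials. Over the whole rule, the loss is then about 1 point (normal), 6 (lognormal), 1 (t, 5 df) and under 1 (t, 3 df). If normality is judged on the raw values, the lognormal loss is about 11 points (81% against 92%). In each of these cases overall power stays above 80%. This stands, with one limit: an outcome classed as non-parametric by its type, such as an ordinal questionnaire score, would always go to the rank test. No loss was computed for such outcomes.
- **The correlation is weakly supported.** This also stands. G1 does not say that its effect size uses the SD of the differences, so the size should be read as a range.
- **The error is conservative, in a 15-person pilot.** True for positive correlation. It limits the seriousness but does not make the named test right. At r = 0, with lognormal data and unequal SDs, Mann-Whitney's type I error is about 7-8%.
- **The signed-rank test has its own weakness.** It assumes roughly symmetric differences. With lognormal sway, equal means, SDs of 0.76 and 0.44, and r = 0.5, its type I error is about 6.5-7%, against about 6.0% for the paired t-test. Part of the lognormal power gap therefore compares tests of different true size. The normal-data gap is not affected: signed-rank stays at about 5% there.

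**Conclusion.** The concern holds: G2 is wrong as written for Phase I. It assigns an independent-samples test to paired data, and no reading of a single-arm phase makes that test appropriate for the 6-week effect.

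For an outcome that is sent to the rank test, the cost is about 20 points of power at r = 0.5 with normal or lognormal data, and about 0 to 28 points for r from 0 to 0.7. Heavy tails reduce it to about 12 or 4 points at r = 0.5. Over the whole two-branch rule the loss is smaller, about 0 to 6 points or up to about 11, depending on how normality is judged. These figures rest on the G1 sway means and SDs and on an assumed correlation. The error can hide a real change; with positive correlation it does not inflate claims of benefit.

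It should be fixed, because an analyst following the text would run the wrong test and the correction is simple. It does not undermine the Phase I design, and it hardly touches the randomised comparison in Phase II.

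**What to change.** In G2:

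1. Name the Wilcoxon signed-rank test as the rank alternative for before-after comparisons in Phase I, and for any unadjusted within-arm comparison in Phase II.
2. Keep the Mann-Whitney U-test for independent groups only: men against women, and arm against arm.
3. State that the choice between t-test and rank test is judged on the within-person differences, not on the raw baseline and follow-up values, and say how it is judged.

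The cost is a short wording edit, with no new data, visits or participants. The edit should acknowledge that the signed-rank test assumes roughly symmetric differences, since sway may be skewed.
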